6 RISKS TO PARTICIPANTS

6.1 HSO staff

The risks of participating in the research itself are considered minimal. Additionally, participating does not include any physical risks. One potential risk is breach of confidentiality, such that unauthorized persons could get access to personal or study-related information. Another potential risk is that staff could feel uncomfortable or anxious about answering some survey questions or having MIBI session recordings rated for fidelity.

6.2 HSO clients

The risks of participating in the research itself are considered minimal. Additionally, participating does not include any physical risks. One potential risk is breach of confidentiality, such that unauthorized persons could get access to personal or study-related information. Another potential risk is that clients could feel uncomfortable or anxious about answering some survey questions or having their MIBI session recorded.

7 CONFIDENTIALITY OF STUDY-RELATED RECORDS

The study will be made available for monitoring, auditing, IRB review, and regulatory inspection by providing direct access to study-related source data. Study-related records identifying research participants will be kept confidential (i.e., will only be accessible to the project's authorized research staff) and, to the extent permitted by applicable laws and/or regulations, will not be made publicly available. All study-related records identifying research participants will be destroyed at the end of the study. Recordings of the MIBI sessions will be stored on a HIPAA-compliant cloud managed by Lyssn, with a back-up copy saved on RTI International's enhanced security network server. Recordings of the MIBI sessions will be stored for the duration of the project and destroyed at the end of the project.

8 STUDY OVERSIGHT

Oversight of the study will be the responsibility of the Principal Investigator, including the identification of any conditions that may require premature termination. The study will be made available for monitoring, auditing, IRB review, and regulatory inspection by providing direct access to study-related source data.

9 MONITORING/REPORTING OF DATA AND SAFETY

Responsibility. The research is believed to pose minimal risk to study participants. The Principal Investigator of the research will be responsible for executing the project's data and safety monitoring plan, which will (1) ensure the integrity and security of study data, (2) safeguard the confidentiality of participant data, (3) monitor participant experiences in the study for evidence of potential danger or abuse of the participants or threat of harm by the participants to themselves or to others, and (4) monitor data for possible adverse effects (AEs) of the study and take steps to remedy any that are found.

Data to be collected and monitored. Staff participant data to be collected are staff surveys and digital audio recordings of MIBI staff participants delivering the MIBI. Client participant data to be collected are client assessments and digital audio recordings of MIBI sessions. The staff survey data, client assessment data, and MIBI session fidelity data will be monitored monthly by the data analysis team.

Safety monitoring. An AE is any untoward or unfavorable medical occurrence in a human subject, including any abnormal sign (for example, abnormal physical exam or laboratory finding), symptom, or disease, temporally associated with the subject's

participation in the research, whether or not considered related to the subject's participation in the research. A serious adverse event (SAE) is one that meets one or more of the following criteria: (1) results in death, (2) is life-threatening (places the subject at immediate risk of death from the event as it occurred), (3) results in inpatient hospitalization or prolongation of existing hospitalization, or (4) results in a persistent or significant disability or incapacity. All research staff will be trained to identify and report AEs and SAEs. Any AE or SAE will be reported to the PI within 24 hours. The PI will record all reported events with start dates occurring from when informed consent is obtained through 7 days (for non-serious AEs) or 30 days (for SAEs) after the last day of study participation. Events will be followed for outcome information until resolution or stabilization. When reporting an AE or SAE, the following will be reported: (1) research protocol information (e.g., title, investigator's name, and IRB number); (2) a detailed description of the adverse event, incident, experience, or outcome; and (3) a description of any changes to the protocol or other corrective actions that have been taken or are proposed in response to the AE or SAE. Additionally, to satisfy the requirement for prompt reporting, we will report unanticipated problems using the following timeline:

- Unanticipated problems that are SAEs will be reported to the IRB within 1 week of the PI becoming aware of the event.
- Any other unanticipated problem will be reported to the IRB within 2 weeks of the PI becoming aware of the problem.
- IRB actions (e.g., approval, violations) will be reported to NIDA as part of the annual progress reports.

10 DATA ANALYSIS PLAN

All analyses will follow the intent-to-treat principle and will be conducted using R, SAS, or Mplus. The distribution of each outcome will be examined before analysis. If a distribution exhibits sufficient nonnormality, we will consider other distributions as an alternative to the normal distribution. Doing so will yield more accurate standard errors and p-values. To assess whether distributional choices were appropriate, we will conduct residual diagnostics. Before fitting mixed effects regression models, we will examine variance partitioning between the levels. Intraclass correlations (ICCs) will be estimated and included in publications. Organized by aim, below are descriptions of the sample size, missing data, power, and analysis plan.

Primary Aim. Analyses on the impact of the P4P strategy (i.e., ATTC+ISF+P4P compared to ATTC+ISF) on staff-level outcomes will be analyzed using a three-level mixed-effects regression model (repeated-measures t nested in staff s nested in organization o) with an appropriate distributional assumption. The primary predictor will be the P4P indicator (an organization-level predictor), and its estimated effect is β_2 . Random intercepts β_{0so} will adjust for organization differences. Random slopes β_{1so} allow for change over time. The basic reduced form of the model is $y_{tso} = \beta_{0so} + \beta_{1so}Time + \beta_2P4P + \epsilon_{tso}$. This model will be generalized with a link function if the outcome y_{tso} is nonnormal. Model comparisons will be used to select an appropriate trajectory shape (e.g., linear, quadratic) for the *Time* variable. A sensitivity analysis will

be conducted for each outcome by adding potential staff-level confounders (e.g., sex, race) to the model.

Secondary Aim. Analyses on the impact of the P4P strategy (i.e., ATTC+ISF+P4P compared to ATTC+ISF) on client-level outcomes will be analyzed using a three-level mixed-effects regression model (clients c nested in staff s nested in organization o), with an appropriate distributional assumption. The primary predictor will be organizational-level condition assignment (ATTC+ISF+P4P condition = 1; ATTC+ISF condition = 0), and its estimated effect is β_2 . Random intercepts β_{0so} will adjust for organization and staff differences. Random intercepts will adjust for organization and staff effects on the relationship between baseline client outcomes and the follow-up outcome β_{1so} . The basic reduced form of the model is $y_{cso(follow-up)} = \beta_{0so} + \beta_{1so}y_{cso(baseline)} + \beta_2P4P + \varepsilon_{cso}$. A sensitivity analysis will be conducted for each outcome by adding potential staff-level and client-level confounders (e.g., sex, race) to the model.

Exploratory Aim. For the exploratory aim, we will use the staff-level data and client-level data used above, as well as the average implementation climate score for each MIBI staff member (i.e., the hypothesized mediator). We will apply a Baron-and-Kenny-style mediation approach, which uses centering within context and includes a group mean at level three. Step 1 is that the outcome will be regressed on the condition variable (ATTC+ISF+P4P condition = 1; ATTC+ISF condition = 0) in a multilevel regression. Step 2 is that the outcome will be predicted by both condition and the group mean-centered mediator (i.e., implementation climate) in a multilevel regression. Step 3 is that the mediational effect will be calculated by subtracting the estimated coefficient associated with condition in Step 2 from the estimated coefficient associated with condition in Step 1. This method will allow the between-group mediation effect to be partitioned from the within-group mediation effect, which is important because between-group mediation is the effect of interest. Significance of the mediation effect will be calculated using the Freedman and Schatzkin t statistic.

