2.2 Implementation outcomes

The SAT2HIV-II Project's four implementation outcomes are:

MIBI implementation consistency: The cumulative number of MIBIs that each MIBI staff member implemented during the implementation phase.

MIBI implementation quality: The cumulative sum quality score that each MIBI staff member demonstrated during the implementation phase. Each MIBI session will be rated using the Lyssn Platform and the Independent Tape Rater Scale.⁶³

MIBI sustainment consistency: The cumulative number of MIBIs that each MIBI staff member implemented during the sustainment phase.

MIBI sustainment quality: The cumulative sum quality score that each MIBI staff member demonstrated during the sustainment phase. Only the Lyssn Platform will be used to rate each MIBI session during the sustainment phase.

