5 STUDY PROCEDURES

5.1 HSO staff

The expected duration of participation for each HSO staff participant is 19 months. Organized chronologically, below are the study procedures. All online staff surveys will be programmed using Voxco.

Complete baseline staff survey. During month 1, all consenting staff participants will be emailed a unique link to the project's online baseline staff survey, which will take about 25 minutes to complete. Each staff participant who completes the baseline staff survey will receive \$25 as compensation.

Complete online introduction to motivational interviewing course. During month 1, all MIBI staff participants will be emailed a link to the project's 5-hour online introduction to motivational interviewing course.

Participate in virtual motivational interviewing training workshop. During month 2, all MIBI staff participants will be emailed a Zoom training link and passcode for each of the project's three 4-hour motivational interviewing training workshops.

Complete follow-up staff survey. During month 2, after the training workshops, all MIBI staff participants will be emailed a unique link to the project's online follow-up staff survey, which will take about 25 minutes to complete. Each staff participant who completes the follow-up staff survey will receive \$25 as compensation.

Submit recording of MIBI roleplay session. Beginning in month 2, after the completion of the project's second motivational interviewing workshop training, all MIBI staff participants will be asked to submit a recording of their MIBI roleplay session that will be conducted with one of their organization's other MIBI staff participants.

Submit recordings of MIBI sessions with client participants. After demonstrating proficiency via a MIBI roleplay session, all MIBI staff participants will be asked to submit a recording for each MIBI session they implement with a client participant.

Review standardized motivational interviewing fidelity feedback reports. Each MIBI session recording will be rated for fidelity, and MIBI staff participants will be asked to review each fidelity feedback report.

Participate in MIBI consultation meetings. Beginning in month 3, all MIBI staff participants will be asked to participate in monthly 30-60-minute virtual group consultation meetings with an MI expert.

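### The primary outcomes are one total per staff member per phase, but the primary model needs repeated measures, and the plan does not say how its P4P coefficient relates to those totals

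*Combined protocol and SAP*

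**What the plan says.** Section 2.2 (Implementation outcomes) defines implementation consistency as "The cumulative number of MIBIs that each MIBI staff member implemented during the implementation phase" and implementation quality as "The cumulative sum quality score that each MIBI staff member demonstrated during the implementation phase". The two sustainment outcomes are worded the same way for the sustainment phase. Each is one number per staff member per phase.

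Section 10 (Data Analysis Plan), Primary Aim, analyses these outcomes with a three-level model, "repeated-measures t nested in staff s nested in organization o". It has random intercepts, random slopes on Time and a P4P (pay for performance) main effect: "The primary predictor will be the P4P indicator (an organization-level predictor), and its estimated effect is" β₂. The printed equation has no P4P-by-Time term. On form, the section adds: "The distribution of each outcome will be examined before analysis"; "This model will be generalized with a link function if the outcome" is nonnormal; and, for Time, "Model comparisons will be used to select an appropriate trajectory shape".

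No section says what y_tso is (phase total, per-period amount, running total or session score), at which occasions it is taken, or how β₂ relates to the phase total. The staff survey months in Section 5.1 and the monthly data monitoring in Section 9 are not tied to it.

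**The concern.** The definition of the outcome and the model for it do not fit together. With one value per person, Time does not vary and a random slope has nothing to act on. The analyst must therefore either set the printed model aside or build a repeated outcome that Section 2.2 does not define. The records allow this, because Section 5.1 says "Each MIBI session recording will be rated for fidelity". But the possible constructions do not all estimate the same quantity.

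At stake is what the primary test means. Three effects that produce the same phase total could give a β₂ near zero, negative or positive. For quality, modelling session scores would test whether sessions are better on average, whereas Section 2.2 asks about the sum. Section 1.2 attaches one bonus to each MIBI (the brief intervention) delivered and another to reaching the quality benchmark, so volume and quality could move separately. The mediation analysis in Section 10 reuses the same staff-level data and would inherit the ambiguity.

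**Working it through.** The plan gives no power or effect figure for this aim, so there is none to reproduce.

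**Step 1. Can the printed model be fitted to the outcomes as defined?** Take a normal model with staff-level intercept variance a, intercept-slope covariance b, slope variance c and residual variance s²:

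- Var(y_t) = a + 2bt + ct² + s²
- Cov(y_t, y_u) = a + b(t + u) + ctu for t ≠ u

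That is four parameters. T occasions supply T(T+1)/2 distinct moments.

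- T = 1 (the phase total): 1 moment, so not identified.
- T = 2 (treating the two phases as occasions): 3 moments, still not identified. A Poisson model has no free residual variance, so this line applies to the normal model only.
- T = 3: 6 moments of rank 4, so identified.

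**Step 2. What does β₂ estimate if monthly records are used?** From the documents: 30 sites (Section 1.2). Everything else is assumed, because the documents give no staff numbers, rates, ICCs or phase lengths: 15 organizations per arm, 3 staff each, 6 months, control rate 1 MIBI per month, rate ratio averaging 1.5, log-SD 0.3 between organizations and 0.5 between staff.

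- Mean control rate: exp((0.3² + 0.5²)/2) = exp(0.17) = 1.185 per month.
- Constant effect: monthly difference 1.185 × 0.5 = 0.593; phase total 6 × 0.593 = 3.56.
- Building effect (ratio 1.0, 1.2, …, 2.0): 1.185 × (0 + 0.2 + 0.4 + 0.6 + 0.8 + 1.0) = 3.56. Fading is the mirror image, with the same total.

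With balanced arms and no P4P-by-Time term, β₂ = 1′V⁻¹d / 1′V⁻¹1. Here d holds the arm differences by month and V is the fitted covariance of an organization's mean profile. I took V as the large-sample fit with correlated random intercepts and slopes at both levels, identity scale, linear Time.

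| Effect (total 3.56, monthly mean 0.59) | β₂, running total | β₂, monthly count |
|---|---|---|
| Constant | 0.13 | 0.59 |
| Building | -0.70 | 0.25 |
| Fading | 1.03 | 0.25 |

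The random slopes absorb much of any arm difference that changes over time, so β₂ is weighted away from the months in which the arms have diverged. Simulation agrees: running total 0.15, -0.67 and 1.05; monthly count 0.30 for the building effect. For a constant effect, simulated power was 8% for the running total and 58.5% for a t-test on organization means of phase totals. For the building effect, it was 28% for monthly counts and 58% for the phase total.

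**Step 3. Log link, consistency counts.** With a Poisson mixed model and a constant effect, power was 61% for running totals and 61% for monthly counts, against 62% for a negative binomial model of the phase total. A second set of simulations (200 runs per cell, error about 3.5 points) covered all three effect shapes. It gave 56% to 65% for the log-link models and 58% to 63% for the phase-total t-test. The two sets differ for monthly counts under building and fading effects (67% and 69% against 56% and 56%), so I conclude only that there was little or no loss.

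**Step 4. Quality, sum against session score.** Assumed: 50 points per session, session SD 10, staff SD 5; 200 runs.

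| Scenario | Phase sum: difference, power | Per-session β₂, power |
|---|---|---|
| More sessions only (ratio 1.5) | +176, 63% | -0.07, 3.5% |
| Better sessions only (+3 points) | +26, 6.5% | 2.9, 49% |

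The expected sums are 50 × 3.56 = 178 and 3 × 6 × 1.185 = 21, so the simulated differences are of the right size.

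**The case against.** The strongest reply is that the harm is confined to particular readings. Section 10 undertakes to examine distributions, to use a link function where needed and to compare time shapes. A sparse monthly count is just the case that this wording covers, and with a log link the consistency outcomes lose little. The identity-scale figures all use linear Time. They also need correlated random effects: with uncorrelated effects and centred Time, monthly counts gave β₂ of 0.59 and 58% power under a building effect, and running totals gave 55% under a constant effect. The plan calls its equation a basic form, and per-session modelling of quality would itself depart from Section 2.2.

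Most of this stands, and it limits the size of the point. Time coding and random-effect covariance are secondary details, and I do not list them as separate defects. What the reply does not supply is a definition of y_tso or a link from β₂ to the phase total. Nor do the log-link results, which concern counts, settle the two quality sums.

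A reader might infer two stronger things. One is that the primary analysis is impossible, or bound to miss a real effect. The documents do not support that: session records could supply repeated measures, and several constructions work well. The other is that the plan permits a choice among definitions once results are known. Section 10 leaves the distribution and time shape open to the data, but it describes no selection among definitions of the outcome.

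**Conclusion.** The point holds as a mismatch between the outcome definitions and the primary model. It affects all four primary outcomes and should be settled before outcome data are seen. That the model cannot be fitted to one total per person follows from the text and needs no assumed inputs.

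The consequences do depend on assumptions. On the identity scale with correlated random effects, β₂ is not the phase-total effect. For one and the same true total, its sign on running totals depends on the shape of the effect. On monthly counts it matches the true mean for a constant effect and is less than half of it (0.25 against 0.59) for a building or fading one. The log link removes most of this for the consistency counts. For quality, session-level and phase-sum analyses answer different questions. The inputs are illustrative, so the figures show direction and rough size only; they do not predict this trial's power.

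**What to change.** Before outcome data are seen, make the primary analysis of each outcome one phase total per staff member, zeros included, with staff nested in organization and β₂ as the P4P effect.

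- **Consistency counts:** negative binomial with log link. Its null rejection rate was 5.8% in 600 simulated runs under the assumed inputs.
- **Quality sums:** prespecify a distribution that allows zeros and skew, or compare organization means.
- **Mean quality per session:** report as a separate prespecified analysis, labelled as average quality.

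An alternative is to keep the three-level model with y_tso defined as the per-period amount, add P4P-by-Time, and test the phase-average contrast. Simulated power was then 58%, 57% and 58% for constant, building and fading effects (identity scale, centred Time).

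The change is to SAP wording and needs no new data, but it has costs. With phase totals the time trajectory becomes descriptive. Differing start times (Section 5.1 requires roleplay proficiency before client sessions) and staff departures count in the total. The quality-sum test will mainly reflect session volume: with better sessions only, power was 6.5%, against 49% for the per-session analysis. That is why the separate quality analysis is needed.

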supported, and rewarded)⁵⁶ mediates the implementation condition to outcome relationship. We focus on implementation climate for several reasons. First, numerous implementation researchers have hypothesized implementation climate as the key construct that may explain the impact of implementation strategies on implementation effectiveness.⁵⁷⁻⁶¹ Second, implementation climate is one of the few constructs that has a psychometrically sound and pragmatic measure available.⁶² Third and most importantly, the P4P strategy is specifically designed to enhance the dimension of implementation climate that may not be addressed by the ISF strategy (i.e., reward). *Thus, this exploratory aim will help advance knowledge by improving understanding regarding the extent to which implementation climate is a key mechanism of change.*

Public Health Relevance

There is an urgent public health need to end the HIV epidemic and more broadly to identify effective strategies to overcome (not just understand) barriers to implementing and sustaining EBHIs in practice settings. The proposed MIBI for substance misuse has been shown to be effective for reducing substance misuse. Additionally, the ATTC+ISF strategy has been shown to be an effective strategy for implementing this MIBI within HSOs. However, even with the ATTC+ISF strategy, room for improvement remains, especially regarding sustainment. Given P4P has been shown to be highly effective, it may be an effective adjunct to the ATTC+ISF strategy (i.e., ATTC+ISF+P4P strategy > ATTC+ISF strategy). However, due to the strength of the research design (i.e., a 30-site, cluster-randomized, type 3 hybrid trial), we believe implementation research will be advanced significantly even if our hypothesis is not supported (i.e., if the ATTC+ISF+P4P strategy is not able to significantly improve implementation outcomes or client outcomes beyond the ATTC+ISF strategy).

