1.2 Study synopsis

The SAT2HIV-II Project is a prospective 30-site cluster-randomized type 3 hybrid trial that is regulated by the Department of Health and Human Services and focused on testing the effectiveness of a Pay For Performance (P4P) strategy as an adjunct to the multifaceted ATTC+ISF strategy, which Garner et al. (2020) found to be the most effective strategy for integrating a MIBI for substance misuse into HSOs. The control condition, which will be provided to all participating HSOs, consists of the following for MIBI staff: 1) a 5-hour online introduction to MI course, 2) three 4-hour virtual training workshops that are focused on the MIBI, 3) standardized feedback reports regarding the fidelity with which each MIBI was implemented, 4) monthly 30-60-minute virtual group consultation calls with an MI expert regarding how to improve fidelity, and 5) monthly 30-60-minute virtual ISF team meetings with an implementation expert. In addition to these strategies, MIBI staff at HSOs randomized to the experimental condition will have the opportunity to earn a \$10 bonus for each MIBI implemented, as well as an additional \$10 bonus for each MIBI that is rated as meeting or exceeding the quality benchmark (i.e., 80th percentile fidelity score from the SAT2HIV-I Project). For leadership staff at all participating HSOs regardless of condition, participation consists of monthly 30-60-minute virtual ISF team meetings with an implementation expert. Other procedures that are included for research purposes only are online surveys with consenting staff and client participants.

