2 OBJECTIVES & OUTCOMES

2.1 Objectives

The objective of the SAT2HIV-II Project is to test the effectiveness of P4P in improving implementation, sustainment, and client outcomes. Specific aims and hypotheses are:

Primary aim: Test the impact of ATTC+ISF+P4P on *implementation outcomes*.

Primary hypothesis: Relative to ATTC+ISF, ATTC+ISF+P4P will achieve significant improvements in staff-level measures of MIBI implementation consistency, MIBI implementation quality, MIBI sustainment consistency, and MIBI sustainment quality.

Secondary aim: Test the impact of ATTC+ISF+P4P on *client outcomes*.

Secondary hypothesis: Relative to ATTC+ISF, ATTC+ISF+P4P will achieve significant reductions in client-level measures of substance use, anxiety symptoms, and depression symptoms.

Exploratory aim: Test the extent to which implementation climate mediates the implementation condition to outcome relationship.

Exploratory hypothesis: Implementation climate will partially mediate the relationship between implementation condition and each of the outcomes in the primary and secondary aims.

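### Exploratory mediation: the Freedman-Schatzkin test can reject up to about 41% of the time when P4P does not move climate, and Step 2 omits the organization-mean climate term

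*Combined protocol and SAP*

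**What the plan says.** Section 10 (Exploratory Aim) takes the average climate score of each MIBI staff member as the mediator and describes a Baron-and-Kenny-style approach, "which uses centering within context and includes a group mean at level three". Step 1 regresses the outcome on condition. Step 2 is itemised as follows: "Step 2 is that the outcome will be predicted by both condition and the group mean-centered mediator (i.e., implementation climate) in a multilevel regression". The mediation estimate, in Step 3, is the Step 1 condition coefficient minus the Step 2 one. The plan says this separates between-group from within-group mediation, "which is important because between-group mediation is the effect of interest". The test is then named: "Significance of the mediation effect will be calculated using the Freedman and Schatzkin t statistic".

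No step regresses climate on condition. No alpha or degrees of freedom are given for this test.

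Section 2.1 states the hypothesis: "Implementation climate will partially mediate the relationship between implementation condition and each of the outcomes in the primary and secondary aims". With the four implementation outcomes of Section 2.2 and the three client outcomes of Section 2.3, that makes seven applications of the test. Section 1.2 describes a "prospective 30-site cluster-randomized type 3 hybrid trial".

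**The concern.** There are two separate problems, and which one applies depends on how Step 2 is coded.

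**If the organization mean is in Step 2**, the Step 3 difference is the right estimate for a linear outcome, but the test is not valid for it. Its denominator treats condition and climate as fixed, so chance differences in climate between the arms are not counted as error. With 30 organizations such differences are sizeable. If climate predicts the outcome, they are read as mediation.

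**If Step 2 is coded as itemised**, the difference cannot reflect the effect the plan wants. Condition varies only between organizations, and a mediator centered within organization varies only within them.

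The background section (1.1) says the aim should help by "improving understanding regarding the extent to which implementation climate is a key mechanism of change". A false positive would credit P4P with working through climate when it had not changed climate. Coding Step 2 as itemised would find no mediation whatever the truth.

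**Working it through.** **Inputs.** From the documents: 30 organizations (Section 1.2); P4P is an organization-level predictor (Section 10, Primary Aim); climate is scored per MIBI staff member (Section 10, Exploratory Aim). Not given, so assumed: 15:15 allocation, two-sided 5%, 28 df, linear normal outcomes, and the staff numbers and climate-outcome associations shown below. The plan states no error rate for this test, so there is no figure to reproduce.

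**Part 1: the test, with the organization mean in Step 2.**

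Let a be the effect of P4P on climate and b the effect of climate on the outcome given P4P. With linear models on organization means, tau - tau' = a × b, where tau and tau' are the condition coefficients in Steps 1 and 2. The statistic is

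t = (tau - tau') / sqrt(s_tau² + s_tau'² - 2 s_tau s_tau' sqrt(1 - r_XM²)),

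where r_XM is the observed condition-climate correlation.

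*One case by hand.* Take a within-arm climate-outcome correlation of 0.6, and suppose climate differs between arms, by chance, by exactly one standard error. Measure everything in units of s_tau.

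- r_XM² = 1/(1 + 28) = 0.0345, so sqrt(1 - r_XM²) = 0.9826.
- s_tau' = sqrt[(1 - 0.36) × (28/27) / (1 - 0.0345)] = 0.8291.
- Denominator = sqrt(1 + 0.8291² - 2 × 0.8291 × 0.9826) = 0.241.
- Numerator = a × b = 0.6, because one standard error of a, multiplied by b, is 0.6 s_tau.
- t = 0.6/0.241 = 2.49, above the critical value of 2.05.

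The test of a itself has t = 1 on 28 df (p about 0.33). An unremarkable chance imbalance is declared significant mediation.

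*Simulated rejection rates with a = 0* (organization means, 40,000 replicates per point):

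| Climate-outcome correlation | 0 | 0.1 | 0.2 | 0.3 | 0.4 | 0.5 | 0.6 | 0.7 | 0.8 | 0.9 |
|---|---|---|---|---|---|---|---|---|---|---|
| Freedman-Schatzkin | 2.0% | 3.4% | 7.6% | 15% | 26% | 37% | 41% | 39% | 31% | 21% |

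Joint significance of a (28 df) and b (27 df) gave 0.2% to 5.0% over the same range. A direct P4P effect on the outcome does not change these rates, because a × b and the residuals do not depend on it.

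*Staff-level check with a = 0* (random-intercept REML, staff within organization, 2,000 replicates per scenario, within-organization slope 0.3, organization SD 0.7):

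| Organization-level climate slope | 0 | 0.2 | 0.4 | 0.6 | 0.8 | 1.0 |
|---|---|---|---|---|---|---|
| 3 staff each | 2% | 12% | 31% | 41% | 38% | 32% |
| 1 to 5 staff | 9% | 22% | 38% | 42% | 37% | 33% |

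The joint test stayed at or below 5.1% in both. With unequal staff numbers the planned test exceeds 5% even at slope 0.

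**Part 2: Step 2 as itemised.**

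The centered mediator sums to zero within every organization, and condition is constant within an organization. The two are therefore orthogonal, and adding the mediator does not move the condition coefficient when staff numbers are equal.

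| True mediated effect 0.80 | Equal staff numbers | 1 to 5 staff |
|---|---|---|
| Step 1 minus Step 2, as itemised | exactly 0.000 | mean 0.000 (SD 0.008) |
| With organization mean added | 0.81 | 0.80 |

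In a separate set-up where the outcome depends on an organization's underlying climate rather than its observed mean (true mediation 0.5, about 3 staff each), the difference was again 0.000 as itemised. It was 0.30 with the organization mean; the shortfall arises because a mean of about three staff is an unreliable measure of organization climate.

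**The case against.** **The two faults cannot both occur.** This is correct. The inflation needs the organization mean in Step 2; the zero difference needs it absent. Coded as itemised, the test rejected only 0% to 2.4% of the time, so 41% does not apply to that reading.

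**The opening sentence already supplies the organization mean.** A careful reader of the whole paragraph might include it. That makes the second fault an inconsistency to reconcile, not proof that the term will be left out. It still needs correcting, because the itemised steps are what gets coded.

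**Step 1 offers some protection.** If mediation were claimed only where Step 1 is significant, and P4P had no direct effect, false positives would fall to 0.1% to 4.8%. But the plan states no such condition, and the partial mediation it hypothesises implies a direct effect. At a correlation of 0.6, direct effects of 0.8 to 1.2 residual SD still leave about 17% to 28%.

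**41% is a maximum.** It needs a correlation near 0.6, and at 0.1 to 0.2 the rate is 3.4% to 7.6%. It also needs P4P to have no effect on climate, which the investigators do not expect, but that is a null the test must control. Rates are 15% or more at every value tabulated from 0.3 to 0.9, and the rationale in Section 1.1 is that climate does drive implementation.

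**The models differ from the plan's.** The plan allows three levels and link functions, and some outcomes are counts. The mechanism is established; the exact rates for those outcomes are not.

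**Conclusion.** The concern holds. With the organization mean in Step 2, the named test is not a valid 5% test of mediation when climate predicts the outcome and P4P leaves climate unchanged. Under the stated assumptions, including no requirement that Step 1 be significant, false rejection rises from 2.0% to a peak of about 41%; a joint test of both paths stays at or below 5.0%. Nothing itemised in the plan tests whether P4P changed climate, so the error would not show directly.

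With Step 2 as itemised, the difference is zero on average and says nothing about between-organization mediation. Taken alone, that is a wording inconsistency.

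The aim is exploratory and no primary or secondary conclusion depends on it. The plan should be changed, but the trial's main results are not at risk.

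**What to change.** 1. In Step 2, list the organization-mean climate score beside the centered score.
2. Add a model of organization-mean climate on condition (path a), and report it.
3. Replace the Freedman-Schatzkin t with a joint-significance test of path a and the between-organization path b, using t reference distributions, or with a Monte Carlo interval for a × b using t draws. State the alpha and degrees of freedom.

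Under the organization-mean set-up above, the two recommended methods rejected at most 5.0% and 5.3%. A percentile organization-level bootstrap gave 0.7% to 7.8%, and a Monte Carlo interval with normal draws up to 6.3%. Both are far better than the planned test, but second choice with 30 organizations.

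The cost is SAP text and a few lines of code; no further data are needed. Nominal power falls. If P4P raises climate by 0.8 SD and the climate-outcome correlation is 0.5, power is 45% for the joint test and 40% for the t-draw interval, against 75% for the planned test. That 75% comes from a test that does not hold its error rate, so it is not a fair benchmark.
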